The multiple-dose pharmacokinetics of BMS-626529 and RTV will be described by summary statistics for the pharmacokinetic parameters by regimen group, study day, antiretroviral treatment history (ARV naive, ARV experienced, and combined [ARV naive + ARV experienced]). Point estimates and 90% confidence intervals will be constructed for accumulation indices (ratio of day 8 vs. day 1 for AUC(TAU), C_{max} and C_{trough}) by regimen group. These estimates will be generated using general linear models fitted to log-transformed data. Similar analysis will also be used to access the effect of RTV on PK exposure of BMS-626529 and diurnal variation for groups 1, 3, 4 and 5. To assess the dependency of BMS-626529 on dose, scatter plots of C_{max}, AUC(TAU), and C_{trough} versus dose will be provided by day. Time to steady-state will be evaluated by summary statistics of C_{trough} and by plotting geometric mean C_{trough} versus study day.

Protein binding for BMS-626529 will be evaluated by summary statistics and tabulated by regimen group.

The effect of BMS-626529 following multiple regimens of BMS-663068 with and without RTV on PD measures (i.e., CD4+ and CD8+ T lymphocyte counts and percents and the corresponding changes in these parameters from baseline) will be assessed by summary statistics. Scatter plots will be used to assess the relationship between the changes from baseline in plasma HIV RNA and BMS-626529 protein binding adjusted EC₉₀, a threshold of protein binding adjusted EC₉₀ will be determined based on this scatter plot and summary statistics will be provided for the changes from baseline in plasma HIV RNA by regimen group, excluding subjects with protein binding adjusted EC₉₀ above this threshold.

Scatter plots will also be used to assess the relationship between the changes from baseline in plasma HIV RNA and BMS-626529 IQs and to assess the correlation between log₁₀ changes from baseline in HIV RNA and IQs. Summary statistics for exploratory biomarkers and corresponding changes from baseline, or percent changes from baseline as appropriate, will be tabulated by regimen group, study day and time point. Possible associations between changes in exploratory biomarkers of interest and BMS-6603068 dose or exposure will be explored graphically and by suitable statistical models, if appropriate. Some nonlinear models, such as but not limited to generalized least squares, will also be explored. Ad-hoc statistical analysis would be considered.

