RTV. Coadministration of 100 mg RTV with BMS-663068 1200 mg ER tablet Q12h significantly increased BMS-626529 C_{max}, AUC and C₁₂ by 64%, 2.1-fold and 4.1-fold, respectively; the apparent terminal half life was increased from 7 to 15 hours. Diurnal effect on BMS-626529 PK was observed after multiple doses. Compared to morning administration, evening dose of 1200 mg BMS-663068 ER resulted in approximately 43%, 46% and 99% higher BMS-626529 C_{max}, AUC and C_{min}, respectively. In the SAD study, less than ~5% of administered dose was eliminated as BMS-626529 in the urine, suggesting that renal excretion is not an important elimination pathway for unchanged BMS-626529.

For more information regarding clinical study results, please refer to the Investigator's Brochure.⁵

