2.2 Secondary Objectives

Secondary objective(s):

- To assess safety and tolerability of multiple regimens of BMS-663068 with and without RTV in HIV infected subjects
- To assess the effect of BMS-626529 following multiple regimens of BMS-663068 on CD4+ and CD8+ lymphocyte counts and percents
- To assess the PK of BMS-626529 following multiple regimens of BMS-663068 with and without RTV in HIV infected subjects
- To assess the diurnal variation in the PK exposures of BMS-626529 following multiple regimens of BMS-663068 with and without RTV in HIV infected subjects
- To assess the plasma protein binding for BMS-626529

- To assess the relationships between change from baseline in \log_{10} HIV RNA versus Inhibitory Quotient (IQ) and PK exposures for BMS-626529 following multiple regimens of BMS-663068 with and without RTV
- To assess the PK of RTV when coadministered with various regimens of BMS-663068

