4 INVESTIGATIONAL PLAN

4.1 Study Design and Duration

This is a randomized, open label, multiple-dose parallel study. Subjects will undergo screening evaluations to determine eligibility within 35 days prior to study enrollment. Subjects will be admitted to the clinical facility the evening prior to dosing (Day -1). Subjects will be randomized into one of 5 regimen groups: Group 1 - BMS-663068 600 mg Q12H + RTV 100 mg Q12H; Group 2 - BMS-663068 1200 mg QHS + RTV 100 mg QHS; Group 3 - BMS-663068 1200 mg Q12H + RTV 100 mg Q12H; Group 4 - BMS-663068 1200 mg Q12H + RTV 100 mg QAM; Group 5 - BMS-663068 1200 mg Q12H.

Each regimen group will consist of 10 subjects. Subjects in each regimen will be randomized and stratified by prior antiretroviral treatment history (ARV naive versus ARV experienced). ARV naive is defined as; no prior ARV therapy of ≥ 1 week. Each regimen group will contain approximately the same distribution of ARV naive and ARV experienced subjects. No more than 70% of the total population (or within each regimen group) will be ARV naive or ARV experienced. All regimen groups may initiate dosing simultaneously. Subjects will be confined to the clinical facility until Day 11. Subjects will return to the unit on Day 15 for a follow-up visit and on Day 50 for discharge procedures. Subjects may have a ± 3 day window around the discharge visit day (Day 50). Safety assessments consisting of ECGs, vital signs, physical exams and clinical laboratory tests will be conducted at screening and at selected time points throughout the study.

All doses will be administered under fed conditions. Subjects in Group 2 (QHS regimen group) will receive study drug every 24 hours in the evening (PM) from Day 1 to Day 8. Subjects in Group 4 (RTV QAM regimen group) will receive BMS-663068 every 12 hours and RTV every 24 hours in the morning (with BMS-663068) from Day 1 to Day 8. Subjects in Groups 1, 3 and 5 (Q12H regimen group) will receive study drug every 12 hours from Day 1 to Day 8.

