5 TREATMENTS

5.1 Study Treatment

All protocol-specified investigational and noninvestigational products are considered study drug. BMS-663068 will be administered as a tablet formulation. Ritonavir will be administered as a capsule. [Table 5.1A](#) outlines the total dose and number of tablets or capsules per daily dose for each group.

Table 5.1A: Treatment Administration

Group	Study Drug Tablet/Capsule Strength	Number of Tablets or Capsules per time of day	Total Daily Dose
1	BMS-663068 600 mg tablet	1 in AM; 1 in PM	1200 mg
	RTV 100 mg capsule	1 in AM; 1 in PM	200 mg
2	BMS-663068 600 mg tablet	2 in PM	1200 mg
	RTV 100 mg capsule	1 in PM	100 mg
3	BMS-663068 600 mg tablet	2 in AM; 2 in PM	2400 mg
	RTV 100 mg capsule	1 in AM; 1 in PM	200 mg
4	BMS-663068 600 mg tablet	2 in AM; 2 in PM	2400 mg
	RTV 100 mg capsule	1 AM	100 mg
5	BMS-663068 600 mg tablet	2 in AM; 2 in PM	2400 mg

All doses will be administered under fed conditions. In the morning of Days 1 through 8 a standard breakfast meal will be administered as breakfast to subjects in Groups 1, 3, 4, and 5 prior to dosing of study drug. On Days 1 through 8 for all groups, an evening snack (approximately 300 - 350 kcal) will be administered prior to the evening dose of study drug. The meal and snack will be ingested within ~30 minutes and will be completed within ~5 minutes prior to dosing of study drug. At the time of dosing, ~240 mL of water will be administered to the subjects along with the study medication. The BMS-663068 tablet(s) must be swallowed intact and are not to be chewed. The water will be consumed within approximately 5 minutes of dosing. The time of the first dose administration will be called “0” hour (AM for groups 1, 3, 4 and 5; PM for group 2). [Table 5.1B](#) provides a description of a representative standard breakfast.

Restrictions related to food and fluid intake are described in Section [5.5.2](#).

Table 5.1B: Representative Standard Breakfast

Food Item	Calories (kcal)	Fat (g)	Carbohydrates (g)	Protein (g)
1 egg fried	90	7.0	0.4	6.3
2 slices of white bread toasted	129	1.8	24.0	4.0
1 tablespoon jelly	56	Trace	13.8	Trace
8 fluid ounces (237 mL) of whole milk	146	7.9	11.0	7.9
Total Grams (g)	-	16.7	49.3	18.2
Total Calories (kcal)	421	153	197	73
% of Total Calories	100	36	47	17

Source: US Department of Agriculture, Agricultural Research Service. 2007 USDA National Nutrient Database for Standard Reference, Release 21.¹⁹

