8.4.4 Pharmacokinetic Analyses

The multiple-dose pharmacokinetics of BMS-626529 following administration of BMS-663068 with or without RTV will be described by summary statistics for the pharmacokinetic parameters by regimen group, study day, dose time (AM or PM, Groups 1, 3, 4 and 5 only), antiretroviral treatment history (ARV naive, ARV experienced, and combined [ARV naive + ARV experienced]). Medians and ranges will be presented for Tmax. Means and standard deviations will be provided for T-HALF. Geometric means and coefficients of variation will be presented for Cmax, Ctrough, C_{ss,avg}, AUC(TAU), AUC(0-24), CLT/F, V_{ss}/F and AI.

To assess the dependency on regimen, scatter plots of Cmax, AUC(TAU), and Ctrough versus regimen group will be provided by day and dose time (Groups 1, 3, 4 and 5 only). Time to steady-state will be evaluated by summary statistics of Ctrough (following AM doses except Group 2) by study day and by plot of geometric mean Ctrough versus study day.

Protein binding (%) for BMS-626529 will be evaluated by summary statistics and tabulated by regimen group. Inhibitory Quotient (IQ) of Cmax, Ctrough (both on Day 8 following AM regimens except Group 2) and C_{ss,avg} of BMS-626529 (defined in section 8.3.2) will be summarized and tabulated by regimen group.

Point estimates and 90% confidence intervals will be constructed for accumulation indices (ratio of Day 8 [AM doses except Group 2] vs. Day 1 for AUC(TAU), Cmax and Ctrough) by regimen group. These estimates will be generated using general linear models fitted to log-transformed data with study day as a fixed effect, and measurements within each subject as repeated measurements. Point estimates and 90% confidence intervals for differences at the log-scale will be exponentiated to obtain estimates and confidence intervals for ratios of geometric means in the original scale. No adjustments will be made for multiplicity.

Similar analysis will be used to assess the effect of RTV on PK exposure of BMS-626529, by comparing the exposure of BMS-626529 in group 3 vs. group 5 and group 4 vs. group 5 with regimen groups as a fixed effect in the general linear models. The effects of diurnal PK variation (PM vs. AM) will also be assessed by the similar model for

Groups 1, 3, 4 and 5 only with time point (PM or AM) as a fixed effect and measurements within each subject as repeated measurements in the general linear models.

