The multiple-dose pharmacokinetics of RTV when coadministered with various regimens of BMS-663068 will be described by summary statistics for the pharmacokinetic parameters by regimen group, study day, dose time (AM or PM, Groups 1 and 3), antiretroviral treatment history (ARV naive, ARV experienced, and combined [ARV naive + ARV experienced]). Medians and ranges will be presented for T_{max}. Means and standard deviations will be provided for T_{HALF}. Geometric means and coefficients of variation will be presented for C_{max}, C_{trough}, C_{ss}, avg, AUC(TAU), AUC(0-24), CLT/F, V_{ss}/F and AI.

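### The PM-versus-AM diurnal model includes Group 4, which takes ritonavir only in the morning, so that group's ratio mixes time of day with ritonavir timing

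*Protocol*

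**What the plan says.** Section 2.2 makes diurnal variation a secondary objective: "To assess the diurnal variation in the PK exposures of BMS-626529 following multiple regimens of BMS-663068 with and without RTV". Section 8.4.4 gives the analysis. It is a general linear model on log-transformed exposure, with measurements within a subject treated as repeated, for "Groups 1, 3, 4 and 5 only with time point (PM or AM) as a fixed effect". Time point is the only fixed effect named. The synopsis repeats the scope: "effect of RTV on PK exposure of BMS-626529 and diurnal variation for groups 1, 3, 4 and 5". Neither place has a term, exclusion or caveat for Group 4.

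The regimens are in section 4.1 and Table 5.1A. All four groups take BMS-663068 morning and evening. Groups 1 and 3 take ritonavir 100 mg with both doses, and Group 5 takes none. Group 4 takes "RTV every 24 hours in the morning (with BMS-663068"), and so none in the evening.

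For ritonavir's own pharmacokinetics, section 8.4.4 limits the morning/evening summaries to two groups: "dose time (AM or PM, Groups 1 and 3").

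**The concern.** A PM/AM ratio shows diurnal variation only if nothing else that drives exposure changes between the two doses. In Groups 1, 3 and 5 the ritonavir schedule is the same at both. In Group 4 every morning dose comes with ritonavir and every evening dose comes 12 hours after it. The two factors are perfectly aliased within the group, so no fit to Group 4 data alone can separate them.

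The competing effect is large. Section 1.3.4 reports that ritonavir raised BMS-626529 Cmax, AUC and C12 "by 64%, 2.1-fold and 4.1-fold, respectively", which is more than the evening increase reported in the same section (43%, 46% and 99% for Cmax, AUC and Cmin). The two effects act in opposite directions in Group 4: evening dosing raises the ratio, and any loss of boost lowers it. A real evening increase could be hidden or even reversed, and the result would still be reported as diurnal variation.

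**Working it through.** The protocol states no expected diurnal ratio for this trial, so there is no planned figure to reproduce. The size can be illustrated from its Phase I results.

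**Inputs (section 1.3.4)**
- Evening-to-morning ratio d: 1.43 (Cmax), 1.46 (AUC), 1.99 (Cmin), reported for the 1200 mg extended-release dose.
- Ritonavir ratio r: 1.64 (Cmax), 2.1 (AUC), 4.1 (C12, used here for Cmin). The fold increases are read as ratios.

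**Assumptions**
- The two effects multiply, and d is the same with and without ritonavir.
- f is the share of the log-scale boost that is lost at the evening dose. The protocol does not give it, so it is shown from 0 to 1.

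**Group 4 alone:** PM/AM = d / r^f

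| f | Cmax | AUC | Cmin |
|---|---|---|---|
| 0 | 1.43 | 1.46 | 1.99 |
| 0.5 | 1.43/√1.64 = 1.12 | 1.46/√2.1 = 1.01 | 1.99/√4.1 = 0.98 |
| 1 | 1.43/1.64 = 0.87 | 1.46/2.1 = 0.70 | 1.99/4.1 = 0.49 |

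**Break-even**, where the ratio is 1 and the evening increase is fully masked: f = ln d / ln r
- Cmax: 0.358/0.495 = 0.72
- AUC: 0.378/0.742 = 0.51
- Cmin: 0.688/1.411 = 0.49

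Reversal needs a larger loss than this. Full loss (f = 1) is a bound and not an expectation. Section 1.3.4 says that with ritonavir "the apparent terminal half life was increased from 7 to 15 hours", so the boosted morning dose carries over into the evening interval.

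**If the four groups of 10 were pooled**, with Groups 1, 3 and 5 at d: pooled PM/AM = d / r^(f/4)

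| f | Cmax | AUC | Cmin |
|---|---|---|---|
| 0 | 1.43 | 1.46 | 1.99 |
| 0.5 | 1.34 | 1.33 | 1.67 |
| 1 | 1.26 | 1.21 | 1.40 |

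Pooling dilutes the ratio but does not reverse it. Leaving Group 4 out keeps it at 1.43, 1.46 and 1.99 under the same assumptions.

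**The case against.** The best defence is that the objective asks about exposure under several regimens with and without ritonavir, and Group 4's PM/AM ratio correctly describes that regimen. It does, and the ratio is worth reporting. But section 8.4.4 sets it beside three ratios that do not carry the ritonavir difference and gives all four the same name.

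Second, the model is probably fitted by group. It is described as similar to the accumulation model, which is by regimen group, and it names no group term. That is the more natural reading, although the text does not say so. It confines the problem to one group of 10 and makes the pooled table hypothetical. It does not help Group 4's own estimate.

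Third, f may be small. Section 1.3.5 notes that ritonavir inhibits metabolism at low doses and that 100 mg once daily boosts atazanavir. This makes some persistence plausible but does not fix f. The distortion is therefore possible and not certain. An unknown f that cannot be separated from time of day is still the reason the ratio cannot be read as diurnal.

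Fourth, the 43%, 46% and 99% figures are reported without mention of ritonavir, and the protocol gives no diurnal ratio for boosted dosing. This limits the illustration, not the aliasing.

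Fifth, meals also differ. A standard breakfast precedes morning doses, while before evening doses "an evening snack (approximately 300 - 350 kcal) will be administered". So the ratio in Groups 1, 3 and 5 is not purely time of day either. That is true, but it applies to all four groups; ritonavir timing is specific to Group 4.

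Finally, the restriction of ritonavir's own morning/evening summaries to Groups 1 and 3 may only reflect that Group 4 has no evening ritonavir dose to summarise. It is not evidence that the distinction was seen and then dropped.

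**Conclusion.** The point holds. The protocol names Group 4 in a model whose only stated fixed effect is completely confounded, within that group, with ritonavir co-dosing. This follows from the regimen and does not depend on anything a statistical analysis plan (not available here) might add about fitting.

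The size is uncertain. Under the multiplicative assumption, the Group 4 ratio could lie anywhere from 1.43 to 0.87 for Cmax, 1.46 to 0.70 for AUC and 1.99 to 0.49 for Cmin. Losing about half of the log-scale boost would be enough to mask the evening increase in AUC and Cmin; for Cmax it takes about 72%. Any loss biases the ratio downward.

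The consequence is limited to a secondary pharmacokinetic objective: one group's estimate if the model is fitted by group, and a diluted overall estimate if it is pooled. It should be corrected because the present wording would label a combined effect as a diurnal one.

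**What to change.** In section 8.4.4 and the synopsis:

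- Estimate the diurnal (PM versus AM) effect from Groups 1, 3 and 5, and state whether it is by group or pooled.
- Report the Group 4 PM/AM ratio separately, labelled as a combined contrast of time of day and ritonavir timing.
- Optionally, set the Group 4 ratio against the Group 3 ratio. Group 3 takes the same BMS-663068 dose with ritonavir at both times, so the quotient of the two ratios reflects ritonavir timing.

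The cost is wording only. All samples are already scheduled in Table 6.5.1A, and no regimen changes. Fitted by group, nothing is lost. If a pooled estimate is wanted, it uses 30 subjects instead of 40, and its confidence interval on the log scale is about 15% wider (√(40/30) = 1.155, taking the same variability in all groups).

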- To assess safety and tolerability of multiple regimens of BMS-663068 with and without RTV in HIV infected subjects
- To assess the effect of BMS-626529 following multiple regimens of BMS-663068 on CD4+ and CD8+ lymphocyte counts and percents
- To assess the PK of BMS-626529 following multiple regimens of BMS-663068 with and without RTV in HIV infected subjects
- To assess the diurnal variation in the PK exposures of BMS-626529 following multiple regimens of BMS-663068 with and without RTV in HIV infected subjects
- To assess the plasma protein binding for BMS-626529
- To assess the relationships between change from baseline in log₁₀ HIV RNA versus Inhibitory Quotient (IQ) and PK exposures for BMS-626529 following multiple regimens of BMS-663068 with and without RTV
- To assess the PK of RTV when coadministered with various regimens of BMS-663068

Exploratory Objective(s):

- To explore the effect of BMS-626529 following multiple regimens of BMS-663068 with and without RTV on activated (DR+) CD4+ and CD8+ subsets
- To explore the effect of BMS-626529 following multiple regimens of BMS-663068 with and without RTV on neutralizing antibody activity

- To explore the effect of BMS-626529 following multiple regimens of BMS-663068 with and without RTV on HIV co-receptor usage (CCR5 versus CXCR4) and to explore the relationship between HIV co-receptor usage and antiviral activity
- To explore the difference in antiviral activity of BMS-626529 following multiple regimens of BMS-663068 with and without RTV by prior antiretroviral (ARV) treatment history (ARV naive versus ARV experienced)
- To explore the change in viral susceptibility measured by envelope genotype and phenotype

Study Design: This is a randomized, open label, multiple-dose regimens, parallel group study. Subjects will be randomized into one of 5 regimen groups:

- Group 1 - BMS-663068 600 mg Q12H + RTV 100 mg Q12H;
- Group 2 - BMS-663068 1200 mg QHS + RTV 100 mg QHS;
- Group 3 - BMS-663068 1200 mg Q12H + RTV 100 mg Q12H;
- Group 4 - BMS-663068 1200 mg Q12H + RTV 100 mg QAM;
- Group 5 - BMS-663068 1200 mg Q12H.

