6.5 Pharmacokinetic Assessments

6.5.1 Pharmacokinetics: Collection and Processing

Tables 6.5.1A and 6.5.1B lists the sampling schedule to be followed for the assessment of pharmacokinetics. Further details of blood sample collection and processing will be provided to the site in the procedure manual.

Table 6.5.1A: PK Sample Schedule (Groups 1, 3, 4 and 5 Only)

Study Day	Time (Event) Hour	Time (Relative To Last Dose) Hour:Min	BMS-626529 and RTV ^a
1 and 8	0 (pre-AM dose)	00:00	x
1 and 8	1	01:00	x
1 and 8	2	02:00	x
1 and 8	3	03:00	x
1 and 8	4	04:00	x
1 and 8	5	05:00	x
1 and 8	6	06:00	x
1 and 8	8	08:00	x
1 and 8	12*	12:00	^b x
8	13	01:00	x
8	14	02:00	x
8	15	03:00	x
8	16	04:00	^b x
8	17	05:00	x
8	18	06:00	x
8	20	08:00	x
9	0	12:00	x

Table 6.5.1A: PK Sample Schedule (Groups 1, 3, 4 and 5 Only)

Study Day	Time (Event) Hour	Time (Relative To Last Dose) Hour:Min	BMS-626529 and RTV ^a
9	4	16:00	x
9	12	24:00	x
10	0	36:00	x
10	12	48:00	x
11	0	60:00	x
5, 6, 7	0 (pre-AM dose)	00:00	x

*: Samples to be taken before evening dosing

^a RTV will be measured in Group 1, 3 and 4 only

^b Additional blood samples will be drawn on Day 8 for protein binding analysis

Table 6.5.1B: PK Sample Schedule (Group 2 Only)

Study Day	Time (Event) Hour	Time (Relative To Last Dose) Hour:Min	BMS-626529 and RTV
1 and 8	0 (pre-PM dose)*	00:00	x ^a
1 and 8	1	01:00	x
1 and 8	2	02:00	x
1 and 8	3	03:00	x
1 and 8	4	04:00	x ^a
1 and 8	5	05:00	x
1 and 8	6	06:00	x
1 and 8	8	08:00	x
2 and 9	12	12:00	x
2 and 9	16	16:00	x
2 and 9	0 (pre-PM dose Day 2)	24:00	x
10	0	36:00	x

Table 6.5.1B: PK Sample Schedule (Group 2 Only)

Study Day	Time (Event) Hour	Time (Relative To Last Dose) Hour:Min	BMS-626529 and RTV
10	12	48:00	x
11	0	60:00	x
5, 6, 7	0 (pre-PM dose)*	00:00	x

*: Subject will receive study drug in the evening.

a: Additional blood samples will be drawn on Day 8 for protein binding analysis.

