8.3.2 Pharmacokinetic Endpoint(s)

Pharmacokinetics of BMS-626529 and RTV will be derived from plasma concentration versus time data. The pharmacokinetic parameters to be assessed include:

C _{max}	Maximum observed plasma concentration
C _{trough}	Trough observed plasma concentration
T _{max}	Time of maximum observed plasma concentration
AUC(TAU)	Area under the concentration-time curve in one dosing interval
AUC(0-24h)	Area under the concentration-time curve over a 24-hour period following the AM dose (PM for Group 2) on Day 8
C _{ss,avg}	Average steady-state plasma concentration, calculated as $AUC(0-24h)/24$
T-HALF	Terminal half-life (after last dose only)
CLT/F	Apparent total body clearance

V _{ss} /F	Apparent volume of distribution at steady-state
AI	Accumulation index; ratio of AUC(TAU) at steady-state to AUC(TAU) after the first dose
Protein binding (%)	Percent of BMS-626529 that are bound to total plasma proteins
IQ	Inhibitory quotient, calculated as the ratio of BMS-626529 in vivo exposure to in vitro measured protein binding adjusted EC ₉₀ . The following in vivo exposure measures will be used in evaluating IQ: C _{max} , C _{trough} and C _{ss,avg} .

Individual subject pharmacokinetic parameter values will be derived by non compartmental methods by a validated pharmacokinetic analysis program.

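### Group 4 takes ritonavir every 24 h, but Day 1 sampling stops at 12 h: the first-dose ritonavir trough is never observed, and first-dose AUC(TAU) and the accumulation index need an unstated extrapolation

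*Protocol*

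**What the plan says.** **Dosing.** The Synopsis and section 4.1 define the arm as "Group 4 - BMS-663068 1200 mg Q12H + RTV 100 mg QAM". Section 4.1 adds that these subjects take "RTV every 24 hours in the morning (with BMS-663068) from Day 1 to Day 8". Table 5.1A agrees: one RTV capsule in the morning and none in the evening.

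**Sampling.** Group 4 shares its schedule with the twice-daily arms; Table 6.5.1A is headed "PK Sample Schedule (Groups 1, 3, 4 and 5 Only". Its Day 1 rows run from pre-dose to 12 h, and the 12-h row is footnoted "Samples to be taken before evening dosing". Rows from 13 h onwards are for Day 8 only. A footnote confirms that RTV is assayed in Group 4. In the Table 6.1 flow chart the Day 2 PK sample is restricted to Group 2.

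**Parameters.** Section 8.3.2 defines AUC(TAU) over one dosing interval, Ctrough as an observed concentration, and AI as the "ratio of AUC(TAU) at steady-state to AUC(TAU) after the first dose". Section 8.4.4 then states: "The multiple-dose pharmacokinetics of RTV when coadministered with various regimens of BMS-663068 will be described by summary statistics". The list by regimen group and study day includes Ctrough, AUC(TAU) and AI. It limits the AM/PM split for RTV to Groups 1 and 3 but makes no exception for Group 4 in the parameter list.

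**The concern.** The Group 4 schedule fits BMS-663068, whose interval is 12 h, but not RTV, whose interval in that arm is 24 h. The next Group 4 PK sample after 12 h on Day 1 is the Day 5 pre-AM trough, so the second half of the first RTV interval has no data. Group 2, the other arm on once-daily RTV, does have samples at 12, 16 and 24 h after its first dose (Table 6.5.1B).

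At stake is the first-dose side of the RTV description in one of the four RTV arms. If the gap is noticed only at analysis, two improvised answers are possible. A 12-h AUC might be put under a 24-h Day 8 AUC, and the result would sit beside AIs from Groups 1 to 3 that rest on complete intervals. Or the 12-h concentration might be labelled a Day 1 trough and compared with the true 24-h troughs of Days 5 to 8. A later analysis plan can set a derivation rule, but it cannot supply a sample that was not drawn.

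**Working it through.** The protocol gives no figure of its own to reproduce here. The check is one of coverage, followed by an illustration of size.

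**1. Coverage of the 24-h RTV interval after a morning dose**

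| | Samples up to | Share of interval |
|---|---|---|
| Group 4, Day 1 (Table 6.5.1A) | 12 h | 12/24 = 50% |
| Group 4, Day 8 (Table 6.5.1A; Day 9 hour 0 is 24 h after the Day 8 morning dose) | 24 h | 24/24 = 100% |
| Group 2, first dose, given in the evening (Table 6.5.1B) | 24 h | 24/24 = 100% |

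The steady-state numerator of AI is therefore available in Group 4. Only the first-dose denominator is incomplete.

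**2. What that does to each first-dose RTV parameter in Group 4**

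- Cmax and Tmax: obtainable.
- Ctrough: defined as observed, and the end of the interval (24 h) is not sampled, so it is not obtainable.
- AUC(TAU): observed from 0 to 12 h only; the remainder must be extrapolated.
- AI: numerator observed, denominator extrapolated.

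**3. Illustration of size**

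Assumptions: one-compartment model, first-order absorption, linear and time-invariant kinetics. Tmax is 4 h, the non-fasting figure in section 1.3.5, which is given there for a 600 mg oral solution. Half-life is 3 to 6 h; the protocol gives none, so this range is assumed.

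With k = ln 2 / half-life, ka solves ln(ka/k)/(ka − k) = 4. In units where F·Dose/V = 1:

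- C(t) = ka/(ka − k) · [exp(−kt) − exp(−ka·t)]
- AUC(0–T) = ka/(ka − k) · [(1 − exp(−kT))/k − (1 − exp(−ka·T))/ka]
- steady-state AUC over 24 h = 1/k
- true AI = (1/k)/AUC(0–24); unequal-interval ratio = (1/k)/AUC(0–12)

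| Half-life (h) | ka | AUC(0–12) | AUC(0–24) | 1/k | Share after 12 h | True AI | Unequal-interval ratio | C(12)/C(24) |
|---|---|---|---|---|---|---|---|---|
| 3 | 0.270 | 3.458 | 4.250 | 4.328 | 18.6% | 1.02 | 1.25 | 9.8 |
| 4 | 0.347 | 4.418 | 5.592 | 5.771 | 21.0% | 1.03 | 1.31 | 7.1 |
| 5 | 0.409 | 5.174 | 6.822 | 7.213 | 24.2% | 1.06 | 1.39 | 5.1 |
| 6 | 0.462 | 5.782 | 7.935 | 8.656 | 27.1% | 1.09 | 1.50 | 3.9 |

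Example at 6 h: 8.656/7.935 = 1.09, against 8.656/5.782 = 1.50. The last column shows that a 12-h concentration cannot stand in for the 24-h trough.

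**4. Alternatives that keep the intervals equal, same model**

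- Fit a log-linear slope λ to 6, 8 and 12 h and add C(12)·[1 − exp(−12λ)]/λ to AUC(0–12). The result exceeds the true AUC(0–24) by 2% to 4%, and AI becomes 0.98 to 1.07 instead of 1.02 to 1.09.
- Divide AUC(0–12) on Day 8 by AUC(0–12) on Day 1. The ratio is 1.02 to 1.10, within about 0.01 of the true AI.
- The same slope carried to 24 h, C(12)·exp(−12λ), gives 1.2 to 1.9 times the true 24-h concentration. Extrapolation serves the AUC tolerably but the trough poorly.

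**The case against.** The strongest reply is that most of this can be repaired in the derivation. Section 8.3.2 asks for non-compartmental methods and does not forbid extrapolating to the end of the interval. Its restriction of T-HALF to the last dose limits what is reported, not the use of a Day 1 slope. Step 4 shows that such an extrapolation works well for AUC and AI under the model. This stands. A reader might infer that none of the three first-dose parameters can be had at all; the protocol supports that only for the observed trough.

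A reader might also infer that the plan will report an AI of 1.25 to 1.50. It does not say so. AUC(TAU) means one dosing interval on both days, and limiting the RTV AM/PM split to Groups 1 and 3 shows that the authors knew Group 4 has no evening RTV dose. No passage prescribes unequal intervals.

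The illustration has soft inputs, too. The Tmax comes from a 600 mg oral solution rather than the 100 mg capsule, and the half-life is assumed. Constant kinetics is doubtful because section 1.3.5 reports that RTV both inhibits and appears to induce CYP3A, the main enzyme in its own metabolism.

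Finally, the scope is narrow. RTV is described by summary statistics in section 8.4.4; the modelled accumulation ratios with 90% intervals sit in the BMS-626529 text there, although the Synopsis introduces both analytes together. RTV accumulation feeds no group comparison, activity criterion or safety rule.

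What the reply does not remove is the mismatch itself. The protocol promises these parameters for Group 4, states no extrapolation rule, and schedules no sample that would make one unnecessary.

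**Conclusion.** The point holds in limited form. The schedule observes half of the first RTV interval in Group 4. The Day 1 observed Ctrough is lost outright, while Day 1 AUC(TAU) and AI depend on an unstated extrapolation. That conclusion rests only on the dosing, the sampling tables and the definitions, and needs no kinetic assumption.

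The size is modest: one co-administered drug, one arm of 10 subjects, the first-dose side of a descriptive secondary objective. Days 5 to 7 troughs and RTV in Groups 1 to 3 are also untouched, and the primary endpoint is not involved. The inflated ratio marks what one careless choice would produce under the assumptions in step 3, and should not be read as a forecast. The change is still worth making because it is cheap and the lost sample cannot be recovered later.

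**What to change.** In Table 6.5.1A and the Table 6.1 flow chart, add one Group 4 PK sample on Day 2 before the morning dose, 24 h after the first RTV dose. Sections 4.1 and 6.6 already schedule an HIV RNA draw at that moment, so the cost is one extra tube in 10 inpatients. State in section 8.3.2 or 8.4.4 that TAU for RTV in Group 4 is 24 h. Coverage of the first interval then rises from 50% to 100%, and Ctrough, AUC(TAU) and AI can all be derived as defined. The 12 to 24 h segment will rest on its two end points. A 16-h sample, as in Group 2, would describe it better but needs a new venepuncture after the evening dose, so it is not part of this proposal.

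If no sample is added, change the wording only: drop Day 1 Ctrough, Day 1 AUC(TAU) and AI for RTV in Group 4, and report a Day 8/Day 1 ratio of AUC(0–12), labelled as a partial-interval ratio. The price is that Group 4 then has no RTV accumulation index on the same definition as the other arms. Neither option touches dosing.
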